8.2.6 EVENTS OF SPECIAL INTEREST

8.2.6.1 UNEXPECTED ADVERSE REACTION DEFINITION

An unexpected adverse reaction is any untoward and unintended response that is related to the administration of the study drug at any dose that is not consistent with the applicable product information (e.g., investigators brochure for an unauthorized investigational medicinal product or summary of product characteristics for an authorized product).

All suspected unexpected serious adverse reactions (SUSARs) will be the subject of expedited reporting. The UNSW shall ensure that all relevant information about a SUSAR that is fatal or life-threatening is reported to the relevant competent authorities and IEC/IRB within 7 days after knowledge by the UNSW of such a case and that relevant follow up information is communicated within an additional 8 days. All other SUSARs will be reported to the relevant competent authorities and IEC/IRB within 15 days after knowledge by the UNSW of such a case. All investigators should follow up SUSARs until the event is resolved or until, in the opinion of the investigator, the event is stabilized or determined to be chronic. Post study SUSARs that occur after the subject has completed the clinical study must be reported by the investigator to the UNSW.

8.2.7 REPORTING OF PREGNANCY

If a female becomes pregnant during the study, the investigator will notify Azura Ophthalmics immediately after the pregnancy is confirmed and the patient will be exited from the study after appropriate safety follow-up. The investigator will (1) notify the patient's physician that the patient was being treated with an investigational drug, and (2) follow the progress of the pregnancy. The investigator must document the outcome of the pregnancy and provide a copy of the documentation to Azura Ophthalmics.

9 STATISTICAL CONSIDERATIONS

9.1 SAMPLE SIZE DETERMINATION

The sample size is determined empirically.

9.2 POPULATIONS FOR ANALYSES

The safety population will include all treated patients. For safety variables, patients in the safety population will be analyzed by the treatment actually received. The modified intent-to-treat (mITT) population will be comprised of all patients randomized and who have values at

randomization, and at least 1 post-randomization for MGE. All patients in the mITT population will be analyzed by the treatment received. This population will be used for the primary and the secondary efficacy analyses.

The method of Last Observation Carried Forward (LOCF) will be used for efficacy on the mITT population. In these analyses, non-missing values recorded at visit 3 or later will be used to replace missing data at visits where data are not recorded.

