1.2 SCHEMA

Study Design: *Structure:* Single-center, single-masked (the individual(s) performing efficacy and safety measures will be masked to treatment assignment for the patient(s) they are assessing), vehicle-controlled, randomized study. For all dose groups a screening visit will be followed by a baseline visit 14 days later (qualification period). At the end of the qualification period patients who still exhibit signs of MGD and who can comply with dosing instructions at the baseline visit will be enrolled into a 3-month treatment period. At the baseline (Day 0) visit, patients will be randomly assigned in a 2:2:1:1 ratio to receive either AZR-MD-001 1.0% ointment/semi-solid drug or AZR-MD-001 1.0% ointment/semi-solid drug plus Hylo-Forte® or AZR-MD-001 vehicle or AZR-MD-001 vehicle plus Hylo-Forte® for twice-weekly evening administration for 3 months. The study flow is shown in Figure 1.

Duration: The total duration of study is approximately 3.5 months (from screening to study completion).

Study Treatment Groups: AZR-MD-001 ointment/semi-solid drug (1.0%) and AZR-MD-001 ointment/semi-solid drug (1.0%) plus Hylo-Forte®.

Controls: AZR-MD-001 vehicle and AZR-MD-001 vehicle plus Hylo-Forte®.

Baseline Visit: "Vaseline" (AZR-MD-001 Vehicle)

Dosage/Dose Regimen: All study treatments are to be self-administered by the patient twice-weekly in the evening. Where applicable, Hylo-Forte® will be dosed approximately 5 minutes before study ointment.

Randomization/Stratification: At Day 0, patients will be randomly assigned in a 2:2:1:1 ratio to receive either AZR-MD-001 1.0% ointment/semi-solid drug or AZR-MD-001 1.0% ointment/semi-solid drug plus Hylo-Forte® or AZR-MD-001 vehicle or AZR-MD-001 vehicle plus Hylo-Forte® for twice-weekly evening administration for 3 months.

Patients will be stratified by average (i.e., across both eyes) baseline MGS score (MGS score of < 6 or MGS score ≥ 6 and ≤ 12). Both eyes should qualify for the study (i.e., meet the inclusion/exclusion criteria).

Visit Schedule: Six scheduled visits: screening (-2 weeks), baseline (day 0), 2 weeks, 4 weeks, 6 weeks and 3 months. For patients who discontinue the study early, the month 3 visit procedures should be completed.

Study Population Characteristics

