6.1.4 ACQUISITION AND ACCOUNTABILITY

Subjects will be instructed on proper instillation and storage of study drug at the end of the baseline (day 0), 2 weeks, 4 weeks and 6 weeks visits, will be given written instructions and may also watch an instructional video. The used and unused study drug tubes will be collected at each visit from baseline up to and including month 3 to assess dosing. Dosing compliance will be based off of the used and unused tube count. If the subject is less than 80% or more than 125% compliant with dosing based on the expected number of used tubes, then the subject will be deemed non-compliant and a deviation should be recorded.

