6.2 MEASURES TO MINIMIZE BIAS: RANDOMIZATION AND BLINDING

Site personnel conducting efficacy and safety measures will be masked to the treatment assignment for the 3 month treatment period.

Screening numbers will be assigned sequentially by site. At the end of the baseline visit, patients will be given a sequential randomization number which corresponds to a specific medication kit number(s) and type in the randomization log. Designated site personnel will report a medication kit number to use for each patient corresponding to the randomization number and will be responsible for monitoring and documenting patient compliance with dosing at each visit. The individual dispensing drug and monitoring compliance will not be the same person who conducts efficacy or safety measures for a given patient.

Additionally, site personnel will observe patients applying ointment from a tube labelled “Vaseline” at the baseline visit, and will have access to instructional dosing videos.

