7.2 PARTICIPANT DISCONTINUATION/WITHDRAWAL FROM THE STUDY

The investigator and Azura Ophthalmics have the right to withdraw a patient from the study at any time for any reason. When possible, the decision to withdraw a patient from the study should be discussed with the investigator.

Azura Ophthalmics may recommend the site withdraw a participant for the following reasons:

- i. Patient Safety: New data/findings plus a DRC decision from ongoing study AZ201801 indicates it is unsafe to continue patients in that study at a dose and frequency being used in the current study;
- ii. Manufacturing: Any problem identified with clinical supplies that may require stopping of dosing;
- iii. Negligence: A general right to stop a study in the event of overt negligence by either party.

Patients who are withdrawn early from the study should have early exit visit procedures completed at the time of withdrawal, or at their next scheduled visit, whenever possible.

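### Section 9.2 analyses its modified intent-to-treat set by treatment received and fills missing efficacy data by LOCF alone, with no efficacy endpoint designated

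*Combined protocol and SAP*

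**What the plan says.** Section 9.2 defines two sets.

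- **Safety set:** all treated patients. "For safety variables, patients in the safety population will be analyzed by the treatment actually received".
- **mITT set:** randomised patients with a value at randomisation and at least one later value for MGE. "All patients in the mITT population will be analyzed by the treatment received". On its use: "This population will be used for the primary and the secondary efficacy analyses".

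For missing efficacy data in the mITT set, Section 9.2 prescribes LOCF, under which "non-missing values recorded at visit 3 or later will be used to replace missing data at visits where data are not recorded". Sections 9.4.1 to 9.4.7 add no other method and no sensitivity analysis. Section 11.3 says only that missing data will be queried.

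The visit schedule in Section 1.2 reads: "Six scheduled visits: screening (-2 weeks), baseline (day 0), 2 weeks, 4 weeks, 6 weeks and 3 months". The same section has early leavers complete the month 3 procedures. Section 7.2 says that withdrawn patients "should have early exit visit procedures completed at the time of withdrawal, or at their next scheduled visit, whenever possible".

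The objectives (Sections 1.1 and 3), the response measures in the synopsis, the measures in Section 8.1.1 and the analysis in Section 9.4.2 all concern safety and tolerability.

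**The concern.** An intent-to-treat analysis, modified or not, compares patients in the arms to which they were randomised. Section 9.2 keeps the label but applies the grouping rule that is usual for safety. If any patient receives a product other than the one assigned, the efficacy comparison no longer rests on randomisation, and no other planned set restores it.

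LOCF treats an early value as if it had been seen at month 3. That is harmless only if the measure would have stayed where it was. If patients leave at different rates or times in different arms, the error does not cancel between arms. The protocol itself gives a reason to think about dropout: its account of the related contact-lens-discomfort study in Section 4 reports three participants who discontinued because of adverse events (their arm is not stated).

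Finally, these rules serve primary and secondary efficacy analyses that the plan does not define, so it is not fixed in advance which result they govern.

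**Working it through.** The sample size is described as empirical (Section 9.1), with no power, effect size, SD or dropout rate, so there is no planned figure to reproduce. The checks below concern scale and wording.

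**1. Weight of one patient who changes group**

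Inputs: about 30 randomised (Section 5.5), ratio 2:2:1:1 (Section 4.1).

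- Active arms: 30 × 2/6 = 10 each. Vehicle arms: 30 × 1/6 = 5 each.
- One patient is 1/5 = 20% of a vehicle arm, or 1/10 = 10% of an active arm.

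These are arm-size figures, not a forecast that anyone will be moved. Section 6.2 sets the route by which it could happen: "patients will be given a sequential randomization number which corresponds to a specific medication kit number(s) and type in the randomization log". A patient's received product therefore departs from the assignment ordinarily only through a kit error.

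**2. Age of a value carried to month 3**

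Inputs: the six visits in order make visit 3 the week 2 visit. Month 3 is taken as week 12 or 13 (an assumption). Table 1 allows ±7 days at weeks 2, 4 and 6.

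| Last value from | Nominal age at month 3 |
|---|---|
| Week 2 | 12 − 2 = 10 to 13 − 2 = 11 weeks |
| Week 4 | 12 − 4 = 8 to 13 − 4 = 9 weeks |
| Week 6 | 12 − 6 = 6 to 13 − 6 = 7 weeks |

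The nominal range is 6 to 11 weeks. With the windows, the extremes are a week 6 visit held 7 days late, 12 − 7 = 5 weeks, and a week 2 visit held 7 days early, 13 − 1 = 12 weeks. So the range is about 5 to 12 weeks for values from scheduled visits. A value from an unscheduled exit visit could fall outside it.

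**3. Direction of the LOCF bias**

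Take a score where higher is better and patients improve over time.

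- If more active-arm patients leave early, their carried values are too low for month 3, and the difference is understated.
- If more vehicle patients leave early while that arm is also improving, the difference is overstated.
- If active-arm patients leave with an early gain that fades once treatment stops, LOCF keeps the gain, and the difference is overstated relative to what would have been seen at month 3.

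A size would require the time course of the measure and the dropout by arm. The documents give neither.

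**4. Is an efficacy endpoint designated?**

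- Section 9.2 conditions mITT entry on MGE. The abbreviation list (Section 12.10) expands MGE and MGS identically. MGS is also the stratification and subgroup variable (Sections 1.2 and 9.4.5).
- No section names MGE or MGS as an endpoint of this trial, with its eye and visit.
- Section 2.2 names MGS and OSDI as primary efficacy variables, but of an earlier study.

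**The case against.** The strongest reply is that the efficacy paragraph is residual text. No stated objective depends on the mITT set or on LOCF, and deleting the paragraph would dispose of most of the point. This stands as a limit on importance. It does not leave Section 9.2 as it is: the text is current and promises efficacy analyses, so it needs either deletion or repair.

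Kits are linked to randomisation numbers, and nothing in the documents suggests that misallocation is expected. That stands too. The grouping rule may never change a result, but if it does, it changes it in the wrong direction for a set carrying this label.

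Early exits are partly covered. Table 1 heads its last column as both month 3 and exit, and Section 1.2 has early leavers complete those procedures. One may guess that an exit value counts as month 3, but no rule says so.

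Three stronger readings are tempting and are not supported:

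- **That a patient who skips Hylo-Forte would be moved to another arm.** The text does not say this. Section 6.1.4 judges compliance by study drug tubes; for a patient outside its limits, "then the subject will be deemed non-compliant and a deviation should be recorded". It provides for no regrouping.
- **That the safety analysis is unsound for the same reason.** Grouping by treatment actually received is conventional for safety and needs no change here.
- **That the endpoint is wholly unknowable, or that LOCF favours the drug.** MGE/MGS is a visible hint, and the direction of the bias cannot be told from the documents.

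**Conclusion.** The point holds, with limited effect. Two stated rules are unsuitable for the efficacy analyses that Section 9.2 announces: grouping the mITT set by treatment received, and LOCF as the sole method for missing data. The missing designation of an efficacy endpoint, and of the visit to which an exit value belongs, is lack of detail that should be settled at the same time.

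The grouping rule matters only if a received product differs from the assigned one; one such patient would then be 20% or 10% of an arm, on the assumption that 30 patients split exactly by the ratio. The carried-value ages assume month 3 at week 12 or 13. The bias from LOCF has neither a known sign nor a known size. Because the stated objectives are safety and tolerability, none of this bears on the planned safety summaries.

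**What to change.** In Section 9.2, either delete the efficacy text or, if efficacy will be reported:

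1. Analyse the mITT set by the arm assigned at randomisation.
2. Make the main analysis one that uses observed visits without carrying values forward. For a continuous measure this could be a simple repeated-measures model adjusted for baseline. If the small arms do not support that model, use a baseline-adjusted comparison of observed month 3 values.
3. Keep LOCF as a sensitivity analysis.
4. Name the efficacy endpoint and its visit, and state which visit an early-exit value belongs to.

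Leave the safety set as treated.

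The cost is a short protocol amendment with ethics approval under Section 10.1; no visit or measurement is added. The downsides are statistical. The repeated-measures analysis assumes data missing at random, and the comparison of observed month 3 values alone needs a stricter assumption, since it ignores the interim visits of patients who left. With about 5 patients per vehicle arm, any model must be kept simple.

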9.3 PROTOCOL DEVIATIONS

A protocol deviation is any noncompliance with the clinical trial protocol, International Conference on Harmonization Good Clinical Practice (ICH GCP), or Manual of Procedures (MOP) requirements. The noncompliance may be either on the part of the participant, the investigator, or the study site staff. As a result of deviations, corrective actions are to be developed by the site and implemented promptly.

These practices are consistent with ICH GCP:

- 4.5 Compliance with Protocol, sections 4.5.1, 4.5.2, and 4.5.3
- 5.1 Quality Assurance and Quality Control, section 5.1.1
- 5.20 Noncompliance, sections 5.20.1, and 5.20.2.

It is the responsibility of the site investigator to use continuous vigilance to identify and report deviations within 10 working days of identification of the protocol deviation, or within 5 working days of the scheduled protocol-required activity. All deviations must be addressed in study source documents. Protocol deviations must be sent to the reviewing IEC per their policies. The site investigator is responsible for knowing and adhering to the reviewing IEC requirements.

9.4 STATISTICAL ANALYSES

9.4.1 GENERAL APPROACH

In general, continuous data will be summarized with descriptive statistics (number of patients, mean, standard deviation, median, minimum, and maximum) and will be analyzed using analysis of variance (ANOVA) techniques or 2-sample t-tests for between-group comparisons, and paired t-tests for within-group analyses. Categorical variables will be summarized by sample size (N), frequency count, and percent, and they will be analyzed using Pearson's chi-square test or Fisher's exact test (if the expected cell count is less than 5 in 25% or more of the cells). Ordinal variables will be analyzed using the Cochran-Mantel-Haenszel (CMH) or the Wilcoxon rank-sum test for between-treatment comparisons and the sign-rank test for within-treatment comparisons.

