1 PROTOCOL SUMMARY

1.1 SYNOPSIS

| | |
|-----------------------------|---|
| Study Compound(s): | AZR-MD-001 (Selenium Disulfide) |
| Phase: | 2 |
| Objectives: | 
To determine the safety and tolerability of AZR-MD-001 1.0% following evening only dosing for Meibomian Gland Dysfunction (MGD).
 
To determine if dosing Hylo-Forte® approximately 5 minutes before study ointment will enhance either the safety or tolerability of AZR-MD-001 1.0% following evening only dosing.
 |
| Clinical Hypotheses: | 
AZR-MD-001 1.0% ointment/semi-solid drug has an acceptable safety and tolerability profile following twice-weekly evening ocular administration for the duration of the study.
 
Dosing Hylo-Forte® approximately 5 minutes before study ointment will enhance the safety or tolerability of AZR-MD-001 1.0% following evening only dosing.
 |

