1.3 SCHEDULE OF ACTIVITIES (SOA)

Table 1 Schedule of Visits and Procedures

| | Screening/-2 weeks | Day 0 | 2, 4 and 6 weeks | Month 3 (Exit) |
|--|--------------------|----------|------------------|----------------|
| Visit Window | N/A | ± 3 Days | ± 7 Days | ± 7 Days |
| Informed consent/authorization | X | | | |
| Demographics | X | | | |
| Inclusion/exclusion criteria | X | | | |
| Medical and ophthalmic history | X | | | |
| Medication history | X | | | |
| Washout medications | X | | | |
| Best-corrected visual acuity (BCVA) | X | X | X | X |
| Subjective questionnaires including visual analogue scales (VAS) and ocular surface disease index (OSDI) | X | X | X | X |
| Tear evaporation rate | X | X | X | X |
| Non-Invasive Tear Break Up Time (TearScope) | X | X | X | X |
| Lipid layer thickness (LipiView II) | X | X | X | X |
| Tear meniscus height (Oculus Keratograph 5M) | X | X | X | X |
| Tear Break Up Time (TBUT) | X | X | X | X |
| Sodium fluorescein corneal staining, Oxford scale | X | X | X | X |
| Sodium fluorescein staining (Eyelid margin and mucocutaneous junction evaluation) | X | X | X | X |
| Meibomian gland evaluation | X | X | X | X |
| Slit-lamp biomicroscopy (includes eyelid margin) ^a | X | X | X | X |
| Lissamine green conjunctival staining, Oxford scale | X | | X | X |
| Lissamine green staining (Eyelid margin and mucocutaneous junction evaluation) | X | X | X | X |
| Schirmer without Anesthesia | X | X | X | X |
| Intraocular pressure (IOP) | X | | | X |
| Ophthalmoscopy exam | X | | | X |
| Meibography | X | | | X |
| Adverse events/medications/tolerability | X | X | X | X |
| Medication dispensing/return | X | X | X | X |
| Physician Observation of Drug Application Methods | | X | | |

^a a photograph of each eye will be obtained at least once for each patient, and photographs and video recording of any interesting/unusual findings may also be made for documentation and/or follow-up purposes

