As specified in Protocol Amendment # 2 dated January 2019, the primary efficacy variables for MGD included change from baseline to month 3 in Meibomian Gland Score (MGS) and measures of Total Ocular Surface Disease Index (OSDI). Least Square (LS) mean changes from baseline (larger scores signal improvement) for MGS at month 3 were 4.5 ± 2.0 ($p = 0.025$) for the Vehicle Group; 1.2 ± 2.0 ($p = 0.56$) for the AZR-MD-001 0.1% Group (sub-therapeutic dose); 4.9 ± 2.1 ($p = 0.02$) for the AZR-MD-001 0.5% Group; and 12.2 ± 2.4 ($p = < 0.0001$) for the AZR-MD-001 1.0% Group. Total OSDI showed the same pattern of results. Least square (LS) mean changes from baseline (smaller scores signal improvement) for Total OSDI at month 3 were 0.0 ± 3.4 ($p = 0.99$) for the Vehicle Group; 9.5 ± 3.8 ($p = 0.01$) for the AZR-MD-001 0.1% Group; -6.9 ± 4.0 ($p = 0.08$) for the AZR-MD-001 0.5% Group; and -12 ± 5.1 ($p = < 0.01$) for the AZR-MD-001 1.0% Group. The difference of 12 between the Vehicle and AZR-MD-001 1.0% Groups was statistically significant ($p = 0.03$) and the results appear dose responsive.

Ocular irritation, conjunctivitis, and epithelial keratitis were observed in clinical protocol AZ201801. Data review from study AZ201801, up to the Interim Analysis, did not identify any significant and/or unexpected safety or tolerability findings for AZR-MD-001 0.1%, 0.5% or 1.0% (see the Investigator's Brochure for more detail). Some patients did anecdotally report that they

preferred nighttime application over daytime application in the clinic as they experienced better study drug tolerability. Investigators also noted that tolerability was improved for some patients with pre-dosing of an artificial tear.

Based upon positive efficacy and safety results from clinical study MGSS1 for the ocular application of selenium disulfide shampoo (2.5%) and from Clinical Protocol AZ201801 for AZR-MD-001 (0.5% and 1.0%), Azura Ophthalmics is further evaluating the best dosing regimen for AZR-MD-001 (1.0%) ointment/semi-solid drug, surfactant free, in patients with MGD.

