9.4.5 SUB-GROUP ANALYSES

Patients will be stratified by average baseline MGS score (i.e., both eyes should meet the inclusion/exclusion criteria).

Thus, subgroup analyses are planned for the 2 groups defined by the 2 stratification factors:

1. Average MGS score < 6
2. Average MGS score ≥ 6 and ≤ 12

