12.10 ABBREVIATIONS

| | |
|---------|--|
| AE | Adverse Event |
| ANCOVA | Analysis of Covariance |
| BCVA | Best-corrected visual acuity |
| CFR | Code of Federal Regulations |
| CMH | Cochran-Mantel-Haenszel |
| CONSORT | Consolidated Standards of Reporting Trials |
| DED | Dry Eye Disease |
| EC | Ethics Committee |
| FDA | Food and Drug Administration |
| GCP | Good Clinical Practice |
| HIPAA | Health Insurance Portability and Accountability Act |
| IB | Investigator's Brochure |
| ICH | International Conference on Harmonisation |
| ICH GCP | International Conference on Harmonisation Good Clinical Practice |
| IEC | Independent Ethics Committee |
| IND | Investigational New Drug Application |
| IOP | Intraocular pressure |
| IRB | Institutional Review Board |
| LOCF | Last Observation Carried Forward |
| LogMAR | Logarithm of the minimum angle of resolution |
| MedDRA | Medical Dictionary for Regulatory Activities |
| MGD | Meibomian gland dysfunction |
| MGE | Meibum gland secretion score |
| MGS | Meibum gland secretion score |
| MGYLS | Meibomian Glands Yielding Liquid Secretion |
| MITT | The modified intent-to-treat |
| MOP | Manual of Procedures |
| NAC | N-acetyl-cysteine |
| NCT | National Clinical Trial |
| NIH | National Institutes of Health |
| NIH IC | NIH Institute or Center |
| OSDI | Ocular Surface Disease Index |
| PI | Principal Investigator |
| SAE | Serious Adverse Event |
| SAP | Statistical Analysis Plan |
| SOA | Schedule of Activities |
| SOP | Standard Operating Procedure |
| SPEED | Eye Dryness questionnaire |
| TBUT | Tear Break-up Time |
| US | United States |
| VAS | Visual analogue scale |

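### Optional improvement: Section 9.4.1 names no MGS stratum term or baseline covariate for between-arm tests, which costs precision but does not cause bias

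*Combined protocol and SAP*

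**What the plan says.** - **Method.** Section 9.4.1 says continuous data "will be analyzed using analysis of variance (ANOVA) techniques or 2-sample t-tests for between-group comparisons, and paired t-tests for within-group analyses". Ordinal data get CMH or Wilcoxon rank-sum tests between treatments. The synopsis and Section 9.4.3 repeat this. Nowhere in Section 9 is a model term, stratification variable or covariate listed.
- **Randomisation.** Section 1.2: "Patients will be stratified by average (i.e., across both eyes) baseline MGS score", with two levels, below 6 and from 6 to 12.
- **Use of the strata.** The only stated analysis use is in Section 9.4.5: "subgroup analyses are planned for the 2 groups defined by the 2 stratification factors".
- **Baseline data.** The schedule in Section 1.3 places BCVA, the questionnaires (OSDI and VAS), meibomian gland evaluation and most other measures at both screening and Day 0. IOP is taken at screening and month 3 only. Section 6.2 states "At the end of the baseline visit, patients will be given a sequential randomization number", so Day 0 values scheduled before that step precede allocation.
- **Sample size.** Section 9.1 sets about 30 patients empirically, with no alpha, power, effect size or SD.

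**The concern.** Stratified randomisation balances the arms on MGS. If MGS predicts the outcome, an unstratified test still counts the between-stratum variation as noise. Its standard error is then too large, its interval too wide, and its type I error below nominal. Similarly, a between-arm test on final values discards whatever the patient's own pre-randomisation value explains, and a change score uses that value inefficiently unless the correlation is high. The paired t-tests use baseline within a group, and the subgroup analyses split the sample; neither adjusts the comparison between arms.

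This matters because the second hypothesis is comparative ("Dosing Hylo-Forte® approximately 5 minutes before study ointment will enhance the safety or tolerability of AZR-MD-001 1.0% following evening only dosing") and rests on about 10 patients per drug arm.

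**Working it through.** **No plan figure to reproduce.** Section 9.1 claims no power, so everything below is illustrative.

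**Inputs from the documents.** N of about 30 at 2:2:1:1 gives 30 × 2/6 = 10 in each drug arm and 30 × 1/6 = 5 in each vehicle arm.

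**Assumptions.** Two-sided alpha 0.05; true difference 1 SD between the two drug arms; baseline-outcome correlation ρ from 0 to 0.7; within-stratum SD 1.

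**Step 1: stratum not prognostic.** Power comes from the noncentral t distribution with noncentrality 1/SE.

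- Final-value t-test: SE = √(2/10) = 0.447, noncentrality 2.236, 18 df.
- Change-score t-test: SE = √[0.2 × 2(1−ρ)], 18 df.
- Four-arm ANCOVA: SE = √[0.2 × (1−ρ²) × 24/23], where 24/23 allows for estimating the covariate slope; 30 − 4 − 1 − 1 = 24 df.
- Two-drug-arm ANCOVA: SE = √[0.2 × (1−ρ²) × 16/15]; 20 − 2 − 1 − 1 = 16 df.

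| ρ | Final value | Change score | Four-arm ANCOVA | Two-drug-arm ANCOVA |
|---|---|---|---|---|
| 0 | 56% | 32% | 56% | 53% |
| 0.3 | 56% | 43% | 60% | 57% |
| 0.5 | 56% | 56% | 68% | 65% |
| 0.7 | 56% | 78% | 84% | 81% |

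Example at ρ = 0.5: four-arm SE = √(0.2 × 0.75 × 24/23) = 0.396, noncentrality 2.53, power 68%. Simulation with assumed permuted blocks of 6 within strata agrees to about a point (four-arm ANCOVA 55%, 60%, 67% and 83%).

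**Step 2: stratum prognostic, ρ = 0.** By simulation, if the strata differ by 1 SD, the t-test has 46–48% power and a model with arm and stratum about 57%. The t-test's type I error falls to about 3%; with the stratum term it stays near 5%. If the strata differ by 0.5 SD, the powers are 53% and 57%. For an assumed five-level ordinal outcome and a 1-SD stratum difference, Wilcoxon gives 42% and van Elteren 50%; with no stratum difference, 52% and 51%.

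**Step 3: the gains overlap.** When one measure is taken twice, its baseline will usually carry the same stratum difference as its outcome. With a 1-SD stratum difference in both, the change-score t-test has about 56% power at ρ = 0.5 and 78% at 0.7, against 67% and 83% for ANCOVA. The stratum term then adds only 1–2 points beyond baseline.

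**Step 4: unequal variances.** If the vehicle-arm SD were half the drug-arm SD, the pooled variance of a four-arm fit would be about (18 × 1 + 8 × 0.25)/26 = 0.77 of the drug-arm variance. The standard error for the drug-arm contrast would then be too small by a factor of √0.77 = 0.88. Simulated type I error is 8–9%. The two-drug-arm ANCOVA holds about 5%.

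**The case against.** **Scope.** The endpoints in Table 3-1 are adverse-event incidence, adverse-event tables and shift tables, and Section 9.4.2 says adverse events are summarised. Covariate adjustment touches none of these. Of the safety measures in Section 8.1.1, BCVA is the only clearly continuous one scheduled at Day 0. This stands and limits the point to continuous and ordinal measures: BCVA, IOP, questionnaire scores, and any efficacy measures analysed under Section 9.2.

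**Latitude.** ANOVA techniques and CMH could carry a stratum. True, but a two-sample t-test cannot, and the plan leaves the choice open.

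**Robustness.** A four-arm ANCOVA is less robust to unequal variances than the t-test already allowed (step 4). This stands and shapes the fix.

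**Readings that go too far.** A reader might set a 46% final-value t-test against 84% for ANCOVA, with stratum and baseline both prognostic at ρ = 0.7. That omits the change-score t-test, equally open under Section 9.4.1, which gives about 65% there. It also assumes baseline unrelated to stratum; without that assumption the gap is 78% v 83%.

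A reader might also infer that ANCOVA was intended and then lost, because "Analysis of Covariance" is in the abbreviation list and Section 2.2 reports "Least Square (LS) mean changes from baseline (larger scores signal improvement) for MGS at month 3" for the AZ201801 study. The list holds other unused entries (SPEED, MGYLS), and Section 2.2 does not state the model behind those means. Neither shows intent.

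**Conclusion.** The point holds as an optional improvement at almost no cost. The plan names no stratum term or covariate, and the information for both is already scheduled. Under the assumptions above, baseline adjustment is worth about 11 points of power at ρ = 0.5 against either t-test. At 0.7 it is worth about 28 points against the final-value test but only about 6 against the change-score test. A 1-SD stratum effect alone is worth about 10 points. These gains should not be added together. None has been shown for this trial, because the documents give no SD, correlation or stratum effect.

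A reader might infer that the planned comparisons are biased or have inflated type I error. They do not: ignoring a prognostic stratum errs on the conservative side, and omitting baseline from a randomised comparison only loses precision. Nor does the plan contradict itself, since it makes no power claim that unadjusted tests would fail to meet.

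**What to change.** In Section 9.4.1, and where the synopsis repeats it:

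1. Analyse each continuous outcome by ANCOVA with arm, MGS stratum and the outcome's own pre-randomisation value: Day 0 where scheduled, otherwise screening (as for IOP). A score with no pre-dose value takes the stratum term only.
2. Stratify the CMH or Wilcoxon (van Elteren) tests by MGS stratum.
3. For AZR-MD-001 1.0% plus Hylo-Forte v AZR-MD-001 1.0% alone, fit the ANCOVA in the two drug arms, or pre-specify that fit as a check on the four-arm model.

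The cost is wording only, with no new data. If neither stratum nor baseline is prognostic, the four-arm model loses about 1 point of power against the t-test (55% v 56% simulated), and the two-drug-arm fit about 3 (53% v 56%). The change does not address missing data.
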